## APPENDIX 4. SCHEDULE OF ASSESSMENTS: WEEK 106 THROUGH WEEK 210/EOS

Assessment a	Treatment Period (Weeks)										Safety Follow-up 210/ EOS
	106, 108, 110, 112, 114	116	118, 120, 122, 124, 126	128	130, 132, 134, 136, 138	140	142, 144, 146, 148, 150	152	154	156	
	158, 160, 162, 164, 166	168	170, 172, 174, 176, 178	180	182, 184, 186, 188, 190	192	194, 196, 198, 200, 202	204	206	208/EOT	
Clinical laboratory assessments b,i		X		X		X		X			X
Vital Signs c	X	X	X	X	X	X	X	X	X	X	
Weight/Height d		X		X		X		X			
Electrocardiogram										X	
Physical Examination e		X		X		X				X	
Muscle function tests f		X		X		X				X	
Pulmonary function tests g		X		X		X				X	
Cardiac MRI i										X	
Muscle MRI i										X	
Specialty labs h										X	X
Pamrevlumab infusion	X	X	X	X	X	X	X	X	X	X j	
Adverse Events & Concomitant	X	X	X	X	X	X	X	X	X	X	X
PODCI Quality Outcome Questionnaire										X	

Abbreviations: MRI, magnetic resonance imaging; PODCI, Pediatrics Outcomes Data Collection Instrument

- a. See [Section 7](#) for details on approved windows, assessments and dosing.
- b. Safety labs: See [Section 7.2.7.1](#). Central labs are required at visits noted in this table.
- c. Vital signs (pulse, respiration, sitting blood pressure, and temperature) to be collected at every visit, and pre-infusion, within 15 minutes of infusion completion and within 15 minutes of completing the observation period.

## Pamrevlumab

## Protocol FGCL-3019-079 Amendment 8

- d. Weight and height (estimated from ulna length) to be measured in screening and approximately every 3 months thereafter.
- e. Physical exam to include assessment of subject's ventilation use. A complete exam is required at Week 208/EOT. Other exams may be disease specific or problem oriented.
- f. Muscle function tests: Brooke Scale, Performance of Upper Limb, Pinch Strength Test, and Grip Test.
- g. Pulmonary Function Tests (PFTs): forced vital capacity, forced expiratory volume in 1 second, maximal inspiratory pressure, maximum expiratory pressure, peak expiratory flow rate, peak cough flow.
- h. See [Section 5](#) for pharmacokinetic/human antihuman antibody/connective tissue growth factor and Exploratory Sample collection details.
- i. Local safety labs required prior to the MRIs and must include hematocrit.
- j. Pamrevlumab infusion is administered at Week 156, but is NOT to be administered at week 208/EOT.

**APPENDIX 5. SPECIALTY LAB SCHEDULE**

Sample	Timepoint	Treatment Period									Safety Follow-up
		Day 0	Day 2 ±1 day	Day 4 ±1 day	Day 7 ±1 day	Day 10 ±1 day	Week 2	Week 26	Week 52	Week 104, 156, 208 /EOT	
Pamrevlumab Pk a	Before infusion	X					X	X	X		
	Within 1 hour after infusion	X							X		
	Time point sample (no infusion)		X	X	X	X					
HAHA b	Predose (when applicable)	X									X
CTGF c	Predose (when applicable)	X								X	
Exploratory d	Predose (when applicable)	X							X	X	

Abbreviations: CTGF = connective tissue growth factor; ET = early termination; HAHA = human anti-human antibody; PK = pharmacokinetic

- a. Approximately 1-2 mL of blood will be collected for each measurement of pamrevlumab PK.
- b. Approximately 1 mL of blood will be collected for each measurement of HAHA.
- c. Blood and urine samples will be collected. Approximately 1 mL of blood and 0.5 mL of urine will be collected for each measurement of CTGF.
- d. Approximately 5 mL of blood will be collected for each exploratory sample.

## APPENDIX 6. OPEN LABEL EXTENSION (OLE)

This is an open-label, single arm extension to evaluate long-term efficacy and safety of pamrevlumab in DMD subjects who have been previously treated with pamrevlumab. Each subject will receive pamrevlumab (35 mg/kg) intravenously, every 2 weeks until the last subject from the phase 3 DMD program completes 52 weeks of treatment on OLE or when pamrevlumab is commercially available or when the Sponsor decides to end the study.

Upon completion of the trial, subjects will be asked to return to the investigative site 4 weeks after their last treatment visit to complete final safety and efficacy assessments with an End of Study Visit, and will receive a final safety follow-up phone call 60 days (+ 3 days) after the last dose.

See parent study protocol for detailed information on study drug formulation, storage, and administration.

### 1. Endpoint

Pulmonary assessment:

- Annual mean change in percent predicted forced vital capacity (ppFVC%) assessed by spirometry.

Performance assessments:

- Annual mean change in the total score of Performance of Upper Limb (PUL).
- Annual mean change the Grip strength of the hands extremities assessed by Hand Held Myometry (HHM).

Cardiac assessments:

- Annual mean change in cardiac fibrosis score assessed by Late Gadolinium Enhancement (LGE).
- Annual mean change in Left Ventricular Ejection Fraction percentage (LVEF %) assessed by MRI.
- Annual mean change in Myocardial Circumferential Strain [Mean Peak Circumferential strain (MPCS) and Global Circumferential Strain (GCS) percentage] assessed by cardiac MRI.

Safety Assessments:

- Adverse events (AEs), serious adverse events (SAEs), clinical laboratory tests and discontinuation of treatment for treatment-related AEs serve as the safety assessments for this OLE.

### 2. Study Enrollment

All subjects participating in the Open Label Extension must have completed treatment through the primary endpoint and completed the EOT visit on the parent pamrevlumab DMD study. The

study investigator must consider the subject medically stable for continued treatment. Written consent/assent by the subject and/or their legal guardian (as required by the site's IRB) must be obtained prior to the subject's participation in the OLE. Administration of current approved DMD therapies is allowed during the OLE treatment period if deemed acceptable by the investigator. Administration of such therapies must be withheld for three hours after the end of pamrevlumab infusion.

### 3. Study Visits

All study visits will be performed in accordance with the Schedule of Assessments presented in [Section 6](#).

The dosing period begins on the first day of dosing with study treatment (Day 0), which is to be conducted simultaneously with, or within 7 days after the parent study EOT visit. The dosing period continues until the last subject from the phase 3 DMD program completes 52 weeks of treatment on OLE or when pamrevlumab is commercially available or when the Sponsor decides to end the study. Subjects will receive study drug every 2 weeks. The visit window for these visits is  $\pm 3$  days. Each visit should be scheduled based on the previous visit, not the Day 0 (baseline) visit.

Muscle or pulmonary function tests that cannot be performed or produce inadequate results according to test procedures during a specified visit should be performed by the next scheduled dosing visit.

Cardiac MRI may be performed within  $\pm 2$  weeks of the specified visit.

Subjects who complete the dosing period must have their end of treatment assessments performed at the Week 208/EOT visit. The end of treatment Cardiac MRI may be performed any time from Week 208/EOT to Week 210/EOS/ET (End of Study / Early Termination) visit.

Subjects who prematurely discontinue the study will be strongly encouraged to complete the final efficacy evaluations scheduled for Week 208/EOT as applicable, and the safety follow-up evaluations scheduled for the Week 210/EOS/ET visit (4 weeks following the last dose) and a final safety follow-up phone call 60 days (+3 days) after the last dose of pamrevlumab as per the schedule of assessments..

For all subjects, the final safety assessments should be completed at the Week 210/EOS/ET visit, 4 weeks ( $\pm 7$  days) after the last dose of pamrevlumab and a final safety follow-up phone call 60 days (+3 days) after the last dose of pamrevlumab as per the schedule of assessments.

In the event that any visit is missed, assessments should be performed as soon after the missed visit as feasible. Missed infusions will not be replaced.

#### 3.1 Home Health Care

FibroGen may consider the use of properly trained home health care staff to administer the pamrevlumab infusions in the future and corresponding study assessments during the conduct of the study, consistent with institutional regulations and policies. Home Health Care (HHC) is optional and the decision to utilize is driven by the site. Subjects who experience a significant infusion reaction will not be allowed to participate in HHC. Medications for the treatment of acute reactions, including anaphylaxis, will accompany the HHC nurse. HHC support will only

be on weeks where no PFT, MFT, safety lab collection, or MRI are being conducted, but only a study drug infusion is occurring.

#### **4. Study Assessments**

All study assessments will be performed in accordance with the Schedule of Assessments presented in [Section 6](#). Refer to the Laboratory Manual for details regarding laboratory sample collection and processing; and the Study Reference Manual for details regarding the conduct of functional tests and MRIs.

Pulmonary function tests (PFTs) will be performed to assess changes in lung function: forced vital capacity (FVC), and peak expiratory flow rate (PEF; PEFR), and forced expiratory volume in 1 second (FEV1).

Performance of the Upper Limb (PUL), and Grip Tests will be performed to assess changes in upper extremity strength and function.

Imaging assessments will be performed to assess changes in Cardiac muscle fibrosis.

A full physical examination will be performed approximately every 24 weeks.

Vital signs (pulse, respiratory rate, sitting blood pressure, and temperature) will be collected at all visits. During infusion visits, vital signs will be collected prior to start of each infusion, within 15 minutes of the end of each infusion, and within 15 minutes of the completion of the post-infusion observation period.

All laboratory tests will be performed at a central laboratory according to the Schedule of Assessments in Section 6. A Central Laboratory Manual with instructions on specimen collection, processing, storing, and shipping to the central laboratory will be provided to all participating sites.

Local clinical laboratories will be used to assess and facilitate the management of adverse events and to provide usual standard of care (including blood draws required prior to MRIs). Local clinical laboratory data will not be collected in the study database except for hematocrit values provided with imaging data.

Safety labs will be drawn at the site's local lab prior to MRIs to ensure there is no contraindication to MRI. Hematocrit should be included in the local lab draw as these results are required to assess fibrosis and will be provided to the central imaging vendor along with the MRI scans. Details are included in the Imaging Manual.

#### **5. Statistical Considerations**

Data collected during the extension period will be summarized descriptively along with the main study.

## 6. OLE Schedule of Assessments: EX – Day 0 through Ex – week 210/EOS/ET

	Treatment Period a					Follow Up Period	
	Day 0 b	Q2 WEEKS: ALL VISITS through Week 206	Q12 weeks through Week 204 (Wk 12, 24, 36, etc.)	Q24 Weeks (Wk 24, 48, 72, etc.)	Q52 weeks through Week 156 (Wk 52, 104, 156, 208 r /EOT)	Wk 210/ EOS/ET p	Final Safety phone call 60 Days (+3 days) after last treatment
Informed Consent & Assent	x						
Eligibility Assessment	x						
Vital Signs c	x	x	x	x	x	x	
Chemistry & Hematology				x		x	
PFT / Height (ulna length) f,h,i				x		x q	
Muscle Function Tests f,g			x	x		x q	
Physical Examination k				x		x	
Weight j	x		x	x			
Weight Based Dose Adjustment j	x		x	x			
Cardiac MRI d,e,f					x	x q	
Specialty Labs o	x					x	
Pamrevlumab Infusion l	x	x	x	x	x		
AEs / SAEs m	x	x	x	x	x	x	x
Concomitant Medications n	x	x	x	x	x	x	x

Abbreviations: AE = adverse event; ECG = electrocardiogram; ET= Early Termination; ICF = Informed Consent Form; PFTs = Pulmonary Function Test;

a.) Visit window of  $\pm$  3 days starting at Week 2.

b.) Day 0 to be conducted simultaneously with, or within 7 days after the parent study EOT visit.

c.) Vital signs (pulse, respiration, sitting BP, temperature) to be collected at every visit: pre-infusion, and within 15 minutes of completion, and within 15 minutes of completing the observation period.

d.) Local safety labs are required prior to MRIs and must include hematocrit.

e.) Cardiac MRI may be performed within  $\pm$ 2 weeks of the specified visit

f.) PFTs, MFTs, and MRI do not require repetition if performed within 4 weeks.

- g.) For Non-ambulatory subjects only: Muscle Function Tests (MFTs): Performance of Upper Limb, and Grip Test.
- h.) Pulmonary Function Tests (PFTs): forced vital capacity, forced expiratory volume in 1 second, peak expiratory flow rate.
- i.) Height will be measured at each PFT interval using ulna length to approximate standing height until subject reaches adult height. Adult height will be carried forward.
- j.) Weight will be measured every 12 weeks to determine dose for the subsequent 12-week interval. Weight is collected during the dose adjustment visit or up to two weeks in advance.
- k.) Full physical exam including chest auscultation
- l.) Pamrevlumab infusion is NOT to be administered at week 208 (EOT)
- m.) AEs and SAEs are collected from date of consent through EOS.
- n.) Concomitant medications and nondrug therapies must be reported beginning after informed consent is obtained and ends 30 days after the last treatment.
- o.) Specialty labs for HAHA (human anti-human antibody) / Neutralizing Antibody
- p.) Subjects who terminate prior to Week 208/EOT should complete the Early Termination (ET) visit.
- q.) Assessment required only if subject terminated study prior to Week 208
- r.) 208 weeks is an estimation of maximum duration for OLE. Actual duration of the OLE will be determined at the Sponsor's program level.

LLN	Lower Limit of Normal for a lab parameter
MAP	Mean Arterial Pressure
MedDRA	Medical Dictionary for Regulatory Activities
MEP	Maximal expiratory pressure
MIF50	Maximal inspiratory flow at 50%

MIP	Maximal inspiratory pressure
mg	Milligram
MMRM	Mixed Model Repeated Measures
MRI	Magnetic resonance imaging
NCI	National Cancer Institute
NCS	Not clinically significant
NYHA	New York Heart Association
OLE	Open label extension
PEF	Peak expiratory flow
PFT	Pulmonary function test
PK	Pharmacokinetic
ppFVC	Percent predicted FVC
PRO	Patient reported outcome
PT	Preferred Term
PTT	Partial prothrombin time
ROM	Range of motion
RPM	Respirations per minute
RCM	Random coefficient model
SAE	Serious adverse event
SAP	Statistical analysis plan
SE	Standard error
SOC	System organ class
SDTM	Study Data Tabulation Model
TEAE	Treatment emergent adverse event
TLFs	Tables, listings and figures
ULN	Upper limit of normal
WHODrug	World Health Organization Drug Dictionary

1. INTRODUCTION

1.1. Preface

This study is a single-arm, open-label extension (OLE) of Study FGCL-3019-079. The OLE period was designed to evaluate the long-term efficacy and safety of pamrevlumab in non-ambulatory DMD subjects who participated in the main phase of the study. Each subject in the OLE will receive pamrevlumab (35 mg/kg) intravenously (IV), every 2 weeks (Q2W) for up to 208 weeks. This dose was a continuation of the dose regimen evaluated during the main study period of FGCL-3019-079. At completion of the OLE subjects will be asked to return to the investigative site to complete final assessments with an End of Study (EoS) visit.

The parent study protocol FGCL-3019-079 provides detailed information on study drug formulation, storage, and administration.

This statistical analysis plan (SAP) summarizes statistical analyses of study data for the subjects who participated in the OLE period of Study FGCL-3019-079.

1.2. Purpose of the Analyses

The analyses will evaluate the long-term efficacy and safety of pamrevlumab in non-ambulatory DMD subjects who participated in the OLE period following completion of pamrevlumab treatment in the main period of FGCL-3019-079.

The OLE data will be summarized as part of the Study FGCL-3019-079 clinical study report.

2. STUDY DESIGN

This study is designed as the open-label extension (OLE) of the main study FGCL-3019-079. All subjects participating in the OLE must have completed treatment through the primary endpoint and completed the End of Treatment (EOT) visit of the main study FGCL-3019-079.

Each subject in the OLE receives pamrevlumab (35 mg/kg, every 2 weeks) for up to 208 weeks. The dosing period began on the first day of dosing with study treatment (Day 1) in the OLE, which is to be conducted simultaneously with, or within 7 days after the parent study EOT visit. The dosing period continued until Week 208/EOT.

3. STUDY OBJECTIVES

3.1. Primary Objective

The primary objective of this trial is to evaluate long-term efficacy and safety of pamrevlumab in non-ambulatory DMD subjects who have been previously treated with pamrevlumab for a minimum of 104 weeks.

4. STUDY ENDPOINTS

4.1. Efficacy Endpoints

The efficacy endpoints are:

Pulmonary assessment:

- Annual mean change in percent predicted forced vital capacity (ppFVC%) assessed by spirometry.

Performance assessments:

- Annual mean change from baseline in the total score of Performance of Upper Limb (PUL).
- Annual mean change from baseline in the grip strength of the hands extremities assessed by Hand Held Myometry (HJM)

Cardiac assessments:

- Annual mean change from baseline in cardiac fibrosis score assessed by Late Gadolinium Enhancement (LGE)
- Annual mean change from baseline in Left Ventricular Ejection Fraction percentage (LVEF %) assessed by MRI
- Annual mean change from baseline in Myocardial Circumferential Strain [Mean Peak Circumferential strain (MPCS) and Global Circumferential Strain (GCS) percentage] assessed by cardiac MRI

4.2. Safety Assessments

Treatment emergent adverse events (TEAEs), serious adverse events (SAEs), clinical laboratory tests and discontinuation of treatment for treatment-related TEAEs serve as the safety assessments for this OLE.

5. GENERAL STATISTICAL CONSIDERATIONS

5.1. Statistical Methodology

Continuous variables will be presented by descriptive statistics: n, mean, standard deviation, median, Q1-Q3, minimum, and maximum. Categorical variables will be tabulated by frequency count and percentage.

Lab results obtained from the central laboratory, rather than local laboratories, will be used for all efficacy and safety analyses. Some lab data are collected using local labs (in lieu of the ICON central lab) due to central lab kit shortages caused by the COVID-19 pandemic. In these cases, local lab values and reference ranges collected from CRFs will be integrated with central lab data when appropriate and feasible. Local lab values will be flagged in data sets and data listings to be differentiated from central lab values. Sensitivity analyses may be performed for key analyses of lab parameters without local lab values (e.g., set to missing).

Unless otherwise stated, all statistical tests will be two-sided hypothesis tests performed at the 5% level of significance for main effects and all confidence intervals will be two-sided 95% confidence intervals.

Unless otherwise specified, there will be no adjustments for multiple comparisons.

All data collected will be presented by data listings for review and substantiation of summary tables.

Safety and efficacy data will be summarized and presented by treatment group (pamrevlumab or source of external data, as applicable), and analysis visit in summary tables as appropriate.

All analyses will be performed using SAS® Version 9.4 or higher.

5.2. Analysis Populations

5.2.1. Safety Population (SAF-OLE)

The Safety population of OLE period (SAF-OLE) consists of all subjects who received at least one dose of study drug in the OLE period. The SAF population will be used in the analyses of all safety parameters.

All analyses for OLE period will be based on SAF-OLE if not specified otherwise.

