9.2.4. Exploratory Analysis - Comparison with the CINRG natural history data

Efficacy endpoints: % predicted FCV (ppFVC), LVEF, and grip strength in dominant hand will be compared with a subset of CINRG DMD Natural History study (DNHS) data with all 36 subjects using a random coefficient model (RCM). The other outcome measures including Performance of Upper Limb (PUL), cardiac fibrosis by LGE, and Myocardial Circumferential Strain [Mean Peak Circumferential strain (MPCS) and Global Circumferential Strain (GCS) percentage] assessed by cardiac MRI are not available in CINRG data and therefore will not be compared.. The RCM model will use efficacy data from both the main and OLE periods and include continuous variable avisityr (calculated as the elapsed days of assessment date from main study baseline date in the unit of year), treatment trt (079 subjects as treated with trt = 1, and subjects in CINRG data as control with trt =0), the interaction term of trt and avisityr, and baseline endpoint as fixed effects, while the intercept and avisityr are included as random effects. The strategy for covariance structure for the within-patient errors in the model is the same as what is described in [Section 9.2.2.1](#). The LSMean (SE) for annual change (slope) as well as LSMean (SE) and 95% CI of treatment differences between pamrevlumab and control of estimated changes from baseline at year 1, year 2, year 3 and year 4 in the OLE period will be presented. The sample SAS code is provided in [Appendix 2](#).

Line plots of each subject's efficacy trajectory compared with the mean plot of the CINRG will be provided.

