APPENDIX 2. SAMPLE SAS CODE FOR RCM ANALYSIS

SAS code for this model, using the primary endpoint ppFVC as example, is provided below.

```

/*Random Coefficient Model (RCM) to estimate the change at year 1, 2, 3 and
4*/
/*avisityr is the actual number of years from Day 1, avisityr=4 will be
the change from baseline at year 4 */
/* fvc0= baseline ppFVC, should be used for change in FVC */
/* &meanfvc0= the mean of the baseline ppFVC           */

proc mixed data = fvc_obs;
  class subjid;
  model chgfvc = avisityr fvc0/solution cl covb outp=pred_fvc cl;
  random intercept avisityr /subject=subjid type=CS;
  ESTIMATE 'Change from Baseline at Year 1' intercept 1 avisityr 1 fvc0
  &meanfvc0 / CL;
  ESTIMATE 'Change from Baseline at Year 2' intercept 1 avisityr 2 fvc0
  &meanfvc0 / CL;
  ESTIMATE 'Change from Baseline at Year 3' intercept 1 avisityr 3 fvc0
  &meanfvc0 / CL;
  ESTIMATE 'Change from Baseline at Year 4' intercept 1 avisityr 4 fvc0
  &meanfvc0 / CL;
  ods output SolutionF=mxparms CovB=mxcovb Estimates=chgfrbl;
run;

```

Sample SAS code for comparison 079 OLE data (trt = 1) with CINRG (trt = 0).

```

PROC MIXED DATA = final;
  CLASS trt SUBJID ;
  MODEL chg = trt|avisityr base/ SOLUTION DDFM=KR;
  RANDOM intercept avisityr / SUBJECT =SUBJID TYPE=UN GROUP= trt;

  LSMEANS trt/ at avisityr = 1 PDIFF CL;
  LSMEANS trt/ at avisityr = 2 PDIFF CL;
  LSMEANS trt/ at avisityr = 3 PDIFF CL;
  LSMEANS trt/ at avisityr = 4 PDIFF CL;

  ods output LSMeans=LSMeans_chg diffss=diffs_chg;
RUN;

```

Statistical Analysis Plan

Addendum

TITLE PAGE

PROTOCOL TITLE: A Trial of FG-3019, a Monoclonal Antibody to Connective Tissue Growth Factor, in Non-Ambulatory Subjects with Duchenne Muscular Dystrophy (DMD)

PROTOCOL NUMBER: Protocol FGCL-3019-079

STUDY SPONSOR: FibroGen, Inc.
[name]
[name]

STUDY DRUG: Pamrevlumab

INDICATION: Duchenne Muscular Dystrophy (DMD)

SAP VERSION Addendum v1.1

RELEASE DATE August 08, 2023

[figure not shown]
CONFIDENTIALITY STATEMENT

The information contained in this document is confidential and proprietary to FibroGen, Inc. No part of this document or any of the information contained herein may be transmitted, disclosed, shared, reproduced, published or utilized by any persons without prior written authorization by FibroGen, Inc.

SIGNATURES AND APPROVALS**Approvals**

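### The exploratory CINRG comparison names no treated analysis set; the SAP default selects OLE entrants, with no corresponding follow-up condition stated for the controls

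*SAP*

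**What the plan says.** SAP section 9.2.4 plans a random coefficient model for ppFVC, LVEF and dominant-hand grip strength. The controls are a "subset of CINRG DMD Natural History study (DNHS) data with all 36 subjects". The treated side is given only as "079 subjects as treated with trt = 1, and subjects in CINRG data as control", with no analysis set named. On data and time, "The RCM model will use efficacy data from both the main and OLE periods", and `avisityr` is "calculated as the elapsed days of assessment date from main study baseline date in the unit of year". The reported results are "estimated changes from baseline at year 1, year 2, year 3 and year 4 in the OLE period".

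Three other places in the SAP bear on who is in the treated arm:
- Section 5.2.1 defines SAF-OLE as subjects with at least one OLE dose and adds "All analyses for OLE period will be based on SAF-OLE if not specified otherwise".
- Section 1.1 says the SAP "summarizes statistical analyses of study data for the subjects who participated in the OLE period".
- The comparison code in Appendix 2 is introduced as "Sample SAS code for comparison 079 OLE data (trt = 1) with CINRG (trt = 0".

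On matching, section 9.2 allows further analyses, only if warranted, that match on baseline prognostic factors under a separate SAP.

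**The concern.** An arm made up of OLE entrants is chosen on what happened during the first two years or more of follow-up, and those same years are then fitted as outcome data. If subjects who declined faster were less likely to enter, the arm is enriched for slow decliners from main-study baseline onward. The mixed model cannot repair this, because the non-entrants' records would not be in the dataset. Neither the treatment-policy rule nor the use of all observed values brings them back. Matching on baseline factors would not remove selection that happens after baseline.

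This is the only between-group comparison specified in the OLE SAP, and its differences carry 95% confidence intervals. Leaving the set unnamed also lets the population be chosen after the main-study results are known: the SAP Addendum says that study has reached database lock and has an interim report.

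**Working it through.** **1. Who is in the treated arm.**

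| Points to OLE entrants only | Allows a wider arm |
|---|---|
| SAP 5.2.1: SAF-OLE default | SAP 9.2.4: refers to 079 subjects and uses both periods |
| SAP 1.1: scope limited to OLE participants | SAP 9.2: refers to participants in the trial generally |
| SAP Appendix 2: code labelled as OLE data | Protocol 9.4: efficacy uses the FAS (not defined in this SAP) |

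Two programmers could build different arms, each consistent with the text.

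**2. What OLE entry selects on.** Withdrawal before Week 104 bars entry (Protocol 7.1.4; SAP 3.1 gives the same minimum). The parent end-of-treatment visit must be complete (SAP 2). The investigator must judge the subject medically stable (Protocol Appendix 6, Study Enrollment). Entry can be later than Week 104, since transition follows approval of the amendment (Protocol 7.1.2) and the main schedule runs on (Protocol Appendix 4). No like condition is stated for CINRG.

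**3. The plan's own figure.** There is no design calculation for this comparison. The main-study one (Protocol 9.1) reproduces by the normal approximation: n = ((1.960 + 0.842) × 5 / 3)² = 21.80, rounded up to 22. With the t distribution, power at 22 is 76.5%, and 24 are needed for 80%. It is used here only for the 22 subjects and for scale: −2 against −5, an effect of 3 points.

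**4. Selection effect by hand.** The documents give no dropout rate, slope SD or link between slope and staying, so all three are assumed. If a fraction q does not enter and the correlation is ρ, the entrants' mean true slope exceeds the full group's by ρ × SD × φ(z_q) / (1 − q). With q = 0.20, φ(z_q) = 0.280 and ρ = 0.5:
- SD 3: 0.5 × 3 × 0.280 / 0.80 = 0.52 points/year.
- SD 5: 0.5 × 5 × 0.280 / 0.80 = 0.87 points/year.

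The fitted estimates differ by less than this, plausibly because early leavers have few visits and carry little weight even when included.

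**5. Difference between the two fitted analyses.** Simulation used 400 datasets per setting and a REML fit of change on group × time and baseline, with random intercept and slope, unstructured by group as in Appendix 2. Assumptions:
- No true effect, both groups at −5 points/year; 22 treated and 36 controls (reading 36 as the CINRG count, since it exceeds both 22 and 32).
- Residual SD 3, also in baseline; the same leaving mechanism in both groups.
- Treated visits every 12 weeks to Week 84, then Week 104, then every 24 weeks to OLE Week 192. For entry at Week 156, visits at Weeks 116, 128, 140 and 156 are added.
- Controls seen every 26 weeks to 6 years.

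Shift in slope difference, OLE-only minus all-treated, over 10–30% gone by Week 104 and slope SD 3 or 5 (points/year):

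| Correlation | Entry at Week 104 | Entry at Week 156 |
|---|---|---|
| 0.3 | 0.06 to 0.35 | 0.11 to 0.65 |
| 0.5 | 0.09 to 0.53 | 0.18 to 0.94 |
| 0.7 | 0.11 to 0.69 | 0.26 to 1.27 |

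At correlation 0 the shift was −0.03 to 0.02 across settings, i.e. none. The Monte Carlo SE is at most 0.043. At the middle setting (20%, 0.5, Week 104) the shift is 0.14 at SD 3 and 0.36 at SD 5; repeat runs of 120 datasets gave 0.12 to 0.14 and 0.32 to 0.35. Against the planning effect this is 0.14 / 3 = 5% to 0.36 / 3 = 12%.

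**6. Error against the truth (zero), Week 104 entry, points/year.**

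| Setting | OLE-only | All-treated |
|---|---|---|
| Middle, SD 3, controls every 26 weeks (two repeat runs) | −0.04, 0.05 | −0.16, −0.09 |
| Middle, SD 5, controls every 26 weeks (two repeat runs) | 0.06, 0.23 | −0.26, −0.13 |
| Middle, SD 3, controls yearly | −0.07 | −0.22 |
| Middle, SD 5, controls yearly | 0.06 | −0.32 |
| 30%, correlation 0.7, SD 5, controls yearly | 0.25 | −0.45 |

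The Monte Carlo SE of the 26-week OLE-only entries is about 0.07 (SD 3) and 0.12 (SD 5). OLE entrants against controls followed to the entry time gave −0.13, −0.13 and −0.05 in the three yearly settings.

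**7. The year label.** Entry needs at least 104 weeks, and 104 / 52 = 2. On an axis starting at main-study baseline, years 1 and 2 therefore fall before or at OLE entry. The Appendix 2 code evaluates `avisityr` at 1 to 4, yet the text places those years in the OLE period.

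**The case against.** The strongest reply is that the default does not govern. It covers analyses for the OLE period unless otherwise specified, while 9.2.4 uses main-study data and refers to 079 subjects without restriction. That reading is open, and it is why the defect is an unnamed set rather than a settled wrong one. A reader should not infer that the SAP fixes an OLE-only arm.

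A reader might also infer that an OLE-only comparison is biased toward pamrevlumab in absolute terms. The evidence does not support that. Step 5 measures the distance between two analyses, and in step 6 at the middle settings the OLE-only estimate is not clearly different from zero and is often nearer to it than the all-treated one. The net direction depends on how the CINRG subset was chosen and how often it was seen. If it was chosen for long follow-up, the all-treated analysis would lean against pamrevlumab.

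Nor can one conclude that the 36 controls were picked without a rule. Main-study SAP version 1.0, cited in the Addendum, is not among the documents supplied and may contain one.

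The upper slope SD leans a little high: with residual SD 3, SD 5 implies an annualised two-year change SD of √(25 + 18/4) = 5.4 against the planned 5. Matching 5 exactly needs √(25 − 4.5) = 4.5, inside the range used. Finally, the comparison is exploratory with no success rule, and Protocol Appendix 6 plans only descriptive OLE summaries. That limits the weight of the point but leaves the ambiguity and the mislabelled years in place.

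**Conclusion.** The point holds as a minor-to-moderate correction to an exploratory analysis. Section 9.2.4 leaves the treated arm unnamed. The SAP's default, scope and code label lead to OLE entrants, an arm selected on events after its own time origin, with no corresponding follow-up condition stated for the controls.

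If faster decliners were less likely to enter, the OLE-only slope difference is more favourable to pamrevlumab than the all-treated one by about 0.14 to 0.36 points/year. That rests on 20% gone by Week 104, correlation 0.5, slope SD 3 to 5 and entry at Week 104, none of which the documents supply. It is zero if every subject entered or if non-entry was unrelated to decline. No false-positive rate is claimed. The conflict between the time origin and the year 1 to 4 label stands whichever population was intended.

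**What to change.** - In 9.2.4 and Appendix 2, define `trt = 1` as all subjects dosed in the main study with a baseline and at least one post-baseline value of the endpoint, using all main and OLE data from main-study baseline.
- Keep OLE entrants as a sensitivity analysis in which CINRG subjects need follow-up to the actual OLE entry time, not simply to 104 weeks. Medical stability cannot be reproduced in CINRG, so this should not become the main analysis. Report both.
- Reword the year 1 to 4 results as years from main-study baseline.
- Report how many main-study subjects did not enter the OLE and why, and state or cite how the CINRG subset was chosen.

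The cost is SAP wording and a re-run on existing data. The estimate may be less favourable. The all-treated analysis can err against pamrevlumab if CINRG visits are sparse or the subset was chosen for long follow-up. The sensitivity analysis loses controls: for entry at Week 104, about 36 × 0.9 = 32, 36 × 0.8 = 29 or 36 × 0.7 = 25 remain at 10%, 20% or 30% dropout.
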